**b) Inclusion and Exclusion Criteria\***

***Inclusion criteria***

- 1) All patients must have a diagnosis of chronic obstructive pulmonary disease and must meet the following criteria: (a) Patients must be in a stable state of their disease with no exacerbation within the previous 4 weeks; and (b) At visit 1 spirometric must demonstrate a post-bronchodilator  $FEV_1 < 50\%$  of predicted normal and a post-bronchodilator  $FEV_1/FVC < 70\%$ .
- 2) At visit 1, patients will demonstrate appreciable reversibility, defined as a 12% increase in  $FEV_1$  in response to albuterol administration.
- 3) Baseline dyspnea index focal score  $\leq 9$ .
- 4) Male or female patients, between 45 and 90 years (inclusive) of age.
- 5) Patients must be current or ex-smokers with a smoking history of more than 10 pack-years
- 6) Patients must be able to perform technically acceptable pulmonary function tests must be able to complete multiple symptom-limited cycle ergometry tests.
- 7) Patients must be able to inhale medication in a competent manner from the inhalers used in the study.

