***Study design***

This will be a randomized, placebo controlled, double-blind study investigating the effects of STIOLTOTTM RESPIMAT® on the mechanisms of exercise intolerance in COPD patients. The study is a crossover, within-patients, design comparing the effect STIOLTOTTM RESPIMAT® to placebo on dynamic hyperinflation, performance fatigue (PF), activation fatigue (AF), and muscle fatigue (MF) during and after constant power exercise to intolerance. Twenty-one patients with moderate to very severe disease will be recruited into this study.

Initially pulmonary function and cardiopulmonary exercise variables will be used to characterize recruited patients. Subsequently, constant power exercise tests (calculated from the initial incremental exercise test to bring the patient to intolerance in approx. 6 min) will be used to characterize the components of performance fatigue, ventilation, dynamic hyperinflation, skeletal muscle oxygenation, and accessory respiratory muscle activity. Patients will perform two

PROTOCOL TITLE: A randomized, crossover, placebo controlled, double-blind phase IV trial of the effect of on STIOLTO™ RESPIMAT® on central and peripheral components of fatigue during exercise in chronic obstructive pulmonary disease  
Revised: November 13, 2015

tests, each to the limit of tolerance, with prior STIOLTO™ RESPIMAT® bronchodilator and placebo. An independent statistician will randomize the order of these two tests, and both patients and investigators blinded to the condition. A pharmacist, who will otherwise not participate in the study, will facilitate drug administration. Unblinding information will be kept in sealed envelopes by the pharmacist in case of (S)AE.

A third constant power exercise test will be performed with the treatment that resulted in the longer endurance time. In this test the components of performance fatigue and dynamic hyperinflation will be measured at the duration at which the patient reached intolerance in the alternative treatment trial (i.e. isotime measurement). This will allow comparisons of PF, AF, and MF and their associations with ventilation, dynamic hyperinflation, skeletal muscle oxygenation, and accessory respiratory muscle activity, between STIOLTO™ RESPIMAT® and placebo at during and following exercise to intolerance and at isotime.

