Visits 3-5: Constant power exercise and fatigue tests. Visits 3-5 will each include spirometry, an exercise test (constant power exercise), and measurement of activation and muscle fatigue, dynamic hyperinflation, ventilation and gas exchange, accessory respiratory muscle activation, and leg muscle deoxygenation. The condition (active drug vs placebo) of visits 3 and 4 will be randomized and each test will be continued to the limit of tolerance. Visit 5 will be an 'isotime' test, in which the patient is stopped at the tolerable duration of the shorter test, using the condition that resulted in the longer duration. Visits 3-5 will be preceded by a 14-day washout period and 7 days using once-daily STIOLTOTTM RESPIMAT® bronchodilator treatment or placebo, with the condition blinded to the patient and investigators. Subjects will take their daily dose of the study medication 90 minutes before undergoing spirometry and constant work rate testing.

Fatigue measurements (particularly AF, and MF) are technically challenging to make, and sometimes a repeat visit is required to secure robust measurements. This occurred in about 15% of visits in our previous study (LA BioMed protocol 30044-01); typically repeated measurements are needed at visit 2 where the patient is initially introduced to the requirement to make a 5-second maximal effort to measure fatigue. Should a repeated visit be necessary, the patient will be continued in the study phase i.e. taking no drug (baseline, visit 2), or taking active drug or placebo (visit 3, 4 or 5). They will be recalled within approximately 1 week for re-testing. On completion of the repeat the subject will then be advanced to the next phase of the study (crossover or isotime).

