### ***Procedures***

An assessment schedule for the procedures in the study is shown in Table 1.

*Pulmonary function*: Visit 1 will include spirometry, lung volume by body plethysmography, and single-breath carbon monoxide diffusing capacity tests. Each will be made according to ATS/ERS guidelines, at least 10 min after 200 µg of albuterol (Millar et al., 2005). Visits 2-5 will include spirometry prior to each exercise test.

*Resting ECG*: Visit 1 will include a resting 12 lead ECG to determine a normal electrocardiogram prior to any exercise testing.

*Medical history and questionnaires*: During visit 1 a medical history will be collected, including respiratory and heart history, smoking history, and medication history. Patients will also complete the St. George's Respiratory

PROTOCOL TITLE: A randomized, crossover, placebo controlled, double-blind phase IV trial of the effect of on STIOLTOT™ RESPIMAT® on central and peripheral components of fatigue during exercise in chronic obstructive pulmonary disease  
 Revised: November 13, 2015

Questionnaire (SGRQ) and the COPD Assessment Tool (CAT) to assess COPD symptoms.

**Table 1.** Assessment Schedule

Study phase	Consent	Screening PFT	Baseline & Randomization	Fatigue test 1	Fatigue test 2	Isotime test
Visit number	-	1	2	3	4	5
Study days	up to -17	-14	0	7	28	49
Inclusion / Exclusion criteria	x	x				
Relevant History, Physical Exam		x				
Height & Weight		x	x	x	x	x
Spirometry		x	x	x	x	x
Lung Volumes		x	x	x	x	x
DL CO		x				
Resting ECG		x				
NIRS Oxidative Capacity Test		x				
CPET & ECG (Incremental)			x			
CPET & ECG (CWR)			x	x	x	x
EMG (Accessory & Leg muscles)			x	x	x	x
Isokinetic Test – Baseline Calibration			x	x	x	x
Isokinetic Test - Fatigue			x	x	x	x
Exercise Leg NIRS			x	x	x	x
Ventilation & Gas Exchange			x	x	x	x
Dynamic Hyperinflation			x	x	x	x
Comments				As required		

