*Incremental exercise test:* All patients will perform a ramp-incremental cycle exercise on an electromagnetically-braked cycle ergometer (Excalibur Sport PFM, Lode NL) to the limit of tolerance after an overnight washout of short-acting bronchodilator (visit 2). Patients will breathe through a mouthpiece with nose clip in place for measurement of respired gases and volumes for breath-by-breath gas exchange and ventilatory measurements (Vmax Spectra, CareFusion USA). Tests will be administered with 3 minutes of rest and at least 3 minutes of unloaded cycling (until a steady-state is achieved), followed by an increase in power output at 5 W/min (for patients with  $FEV_1 \leq 1$  L) or 10 W/min (for patients with  $FEV_1 > 1$  L) and continued to the limit of tolerance. The limit of tolerance will be determined as the point at which the patient experiences intolerable dyspnea or is unable to maintain pedaling rate above 50 rpm despite verbal encouragement. At the limit of tolerance and every 1 minute during recovery an isokinetic power test will be performed (described below). At specified times during the exercise test, inspiratory capacity (IC) measurements will be made using a maximum inhalation. These will be made at rest, every 2 min during exercise, at end-exercise, and every 1 minute during recovery

*Constant work rate (CWR) exercise tests:* From an unloaded pedaling baseline (~3 min), the power output will be abruptly increased to approximately 75% WRpeak (this is the peak work rate achieved during the incremental exercise test). The specific work rate chosen will be chosen to elicit intolerance in ~6 min in the placebo condition (van der Vaart et al., 2013). The patient will be instructed and encouraged to maintain the power output for as long as they can manage (except in the isotime test, as noted below). Patients will breathe through a mouthpiece with nose clip in place for measurement of respired gases and volumes for breath-by-breath gas exchange and ventilatory measurements (Vmax Spectra, CareFusion USA). A familiarization CWR test will be performed at visit 2, at least 1 hour after the incremental test. At specified times during the exercise test, inspiratory capacity (IC) measurements will be made using a maximum inhalation. These will be made at rest, every 2 min during exercise, at end-exercise, and every 1 minute during recovery

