At baseline subjects will cycle at a comfortable cadence with zero load for ~3 min, after which they will be asked to perform 5 pedal strokes (~4 seconds) isokinetic cycling at each of ~25%, ~50%, ~75% and 100% maximal effort. The strain of the task is minimal and only a few seconds (~30 s) recovery is necessary between each effort, but subjects will be given as long as they feel is necessary to recover. During these efforts the flywheel braking of the cycle ergometer is controlled to result in predetermined velocities equating to a constant pedal cadence of 70 rpm. Patients will complete this test twice at baseline (unfatigued condition) prior to each exercise test to ensure reproducibility. If the two repeats do not cohere to within 10%, then the procedure is repeated a third time following a short (~10 min) rest. The patient will then be given 30 minutes to recover before the incremental or CWR exercise test is performed.

During each exercise test, isokinetic fatigue tests will be made at the point of limitation (or at isotime) and during recovery. For this the cycle ergometer will be switched to isokinetic mode and five pedal strokes will be completed at maximal effort (~4 seconds) to determine PF, AF and MF. In order to track fatigue during recovery, 5-pedal-stroke maximal isokinetic efforts will also be made every minute during recovery until the fatigue has recovered to 90% of the baseline value (up to a maximum of 6 minutes; 3-4 minutes is typical).

*Exercise NIRS:* Tissue oxygenation during exercise will be assessed by NIRS (as described above in *Non-invasive assessment of oxidative capacity by NIRS*). NIRS probes will be attached by adhesive tape to the skin of the quadriceps (for muscle oxygenation) and the forehead (for cerebral oxygenation), and a bandage will be placed over the probe to help ensure its stability during exercise.

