**k) Provisions to Monitor the Data to Ensure the Safety of Subjects\***

The data will be handled as source documents. These will include all data with patient demographics, history, questionnaires, pulmonary function, muscle

PROTOCOL TITLE: A randomized, crossover, placebo controlled, double-blind phase IV trial of the effect of on STIOLTOT™ RESPIMAT® on central and peripheral components of fatigue during exercise in chronic obstructive pulmonary disease  
Revised: November 13, 2015

oxidative capacity and exercise testing results. The documents will be filed in the subject's source document binder. This binder will also contain the properly executed consent form, the HIPAA (PHI) form as well as demographic data. The patient identifiers will be kept in this folder, but under a separate section from the study source data. This section will be marked as 'confidential' and the binders will be kept in a locked cabinet in a locked room. Access to the patient identifiers will be permitted only for the study coordinator and the person(s) with direct contact with the patient.

The PI will be responsible for reporting any adverse events to the local IRB utilizing the adverse event reporting policy established by the local IRB. All serious adverse events and non-serious adverse events which are relevant for a reported serious adverse event and Adverse Events of Special Interest (AESI) shall be reported to Boehringer Ingelheim Pharmaceuticals, Inc. Data monitoring will made on a per-procedure basis by the PI or co-investigators.

Per its policy, periodic data monitoring will be undertaken by a member of the Compliance Office at Los Angeles Biomedical Research Institute at Harbor-UCLA Medical Center.

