**20) Sharing of Results with Subjects**

The results of this study will not be shared directly with the participants. As part of the consent process it will be explained to the participants that they can contact the Principal Investigator should they wish to find out about the results of the study, or for any other information about the study.

The results of the pulmonary function tests and cardiopulmonary exercise tests may be shared with the patient on request. Patients are likely to have performed this test previously, and the results of this test may provide information on the progression of their disease. Patients will be provided with a copy of their incremental exercise test results on request. Information on pulmonary function or clinical exercise testing will be provided by the PI or participating physician. Other results will be explained on request by the PI or his staff, but these are experimental procedures and have no specific diagnostic or clinical benefit to the individual patient.

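### The plan states a double blind but has no safeguard against treatment being inferred from visit 3 to 5 lung-function results, which staff may see and patients may request

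*Combined protocol and SAP*

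**What the plan says.** Section 8 g (Study design) describes "both patients and investigators blinded to the condition". The constant work rate text under Procedures extends this to participants and experimenters at visits 3 to 5, up to study end.

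The parts of the plan that bear on whether the blind can hold are these:

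- **Selection.** Section 8 b, inclusion criterion 2: at visit 1 "patients will demonstrate appreciable reversibility, defined as a 12% increase" in FEV1 after albuterol.
- **Untreated reference.** Visit 2 includes spirometry after a 14-day washout of long-acting bronchodilators.
- **Timing.** Visit schedule: "Subjects will take their daily dose of the study medication 90 minutes before undergoing spirometry and constant work rate testing". Procedures: "Visits 2-5 will include spirometry prior to each exercise test". As printed, Table 1 also marks lung volumes at visits 3 to 5.
- **Effort.** For the ride to intolerance, "The patient will be instructed and encouraged to maintain the power output for as long as they can manage". Performance, activation and muscle fatigue (PF, AF, MF) then come from five pedal strokes at maximal voluntary effort.
- **Release to patients.** Section 20: "The results of the pulmonary function tests and cardiopulmonary exercise tests may be shared with the patient on request". The PI or a participating physician gives out the information. No visit is excluded and no waiting period is set.
- **Existing protection.** Matching placebo, randomization codes from an independent statistician, a pharmacist outside the study team, and sealed envelopes (sections 8 g and 17).

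The protocol does not say who performs or reads spirometry at visits 3 to 5, or whether the values are withheld from anyone.

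**The concern.** The existing measures protect the allocation code. They do not stop someone inferring treatment from a measurement that the treatment is meant to change. Section 5 says the drug was chosen to improve lung function acutely, the patients are selected for bronchodilator response, and an untreated value is on file for comparison. Section 20 as written would also let a patient ask for a visit 3 result before visit 4.

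The outcomes are open to such knowledge. Endurance time and the maximal isokinetic efforts depend on will and encouragement. AF is defined as a loss of voluntary activation, and a lower AF at isotime on active drug is the hypothesized result. Endurance at visits 3 and 4 also decides which treatment is taken before visit 5 and sets the isotime, so an influence there carries into the main AF contrast.

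**Working it through.** **Inputs.** The plan has no figure of its own to reproduce here. It gives no FEV1 difference between STIOLTO and placebo, no between-day within-patient SD and no expected rate of correct guesses. The difference D and the SD s below, both as a percentage of FEV1, are therefore assumptions. The 12% row borrows the albuterol entry threshold, which is a different contrast from one week of STIOLTO against placebo. The model takes normal, independent day-to-day variation, no period or carryover effect, and a guesser who uses the best cut-off.

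**Visit 4 against visit 3.** One visit is on drug and the other on placebo, and the guesser calls the higher FEV1 active. The difference has mean D and SD s√2, so

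P(correct) = Φ(D / (s√2)).

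| D | s = 5% | s = 7.5% | s = 10% | s = 15% |
|---|---|---|---|---|
| 6% | 0.80 | 0.71 | 0.66 | 0.61 |
| 12% | 0.96 | 0.87 | 0.80 | 0.71 |
| 20% | >0.99 | 0.97 | 0.92 | 0.83 |

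Worked corners: 6/(15 × 1.414) = 0.283, giving 0.61; 20/(5 × 1.414) = 2.828, giving over 0.99. In the 12% row, 0.71 to 0.96 of 21 patients is about 15 to 20, against 10.5 by chance.

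**Visit 3 against untreated visit 2.** The expected change is D on drug and 0 on placebo, so the best cut is D/2 and

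P(correct) = Φ(D / (2s√2)).

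- D = 12%: 0.80 at s = 5%, 0.73 at s = 7%.
- D = 20%: 0.92 at s = 5%, 0.84 at s = 7%.
- D = 8%, s = 9%: 8/(2 × 9 × 1.414) = 0.314, giving 0.62. Visit 4 against visit 3 gives 0.74 here.
- Weakest corner of the table above (D = 6%, s = 15%): 6/42.4 = 0.141, giving 0.56, little better than chance.

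**From a guess to a bias in AF.** The documents give nothing from which to size this step, so what follows is only a what-if. Section 8 i reports a 33 W AF difference with p = 0.03 in 13 patients given oxygen. Read as a two-sided paired t-test, t on 12 df is 2.461, so the SD of paired differences is 33 × √13 / 2.461 = 48.4 W. If a guess shifted AF by e watts and guesses were right with probability 0.80, the net shift would be (2 × 0.80 − 1)e = 0.6e. The noncentrality of the paired t-test in 21 patients is 0.6e × √21 / 48.4.

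| Assumed e | Net shift | Noncentrality | Two-sided type I error |
|---|---|---|---|
| 5 W | 3 W | 0.28 | 0.058 |
| 10 W | 6 W | 0.57 | 0.084 |
| 20 W | 12 W | 1.14 | 0.191 |

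The result depends entirely on e, which could be close to zero.

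**The case against.** A reader might infer that the person who reads the spirometer coaches the ride moments later, that staff and patients can often tell the treatments apart, or that the plan itself discloses treatment. The documents support none of these.

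- **Reader and coach.** The protocol says only that spirometry precedes the exercise test. Its place among the baseline isokinetic efforts is not given, and after those efforts "The patient will then be given 30 minutes to recover before the incremental or CWR exercise test is performed". Section 7 lists several staff, and nothing says that one person does both jobs. What stands is that nothing prevents it.
- **Data monitoring.** "Data monitoring will made on a per-procedure basis by the PI or co-investigators" appears under subject safety in section 8 k. It does not say that FEV1 is reviewed before the ride or passed to the coach.
- **Patient route.** Section 20 opens by saying that study results are not shared directly with participants, and it promises a copy only of the incremental test, done at visit 2 before any study drug. A mid-crossover release needs both a request and a physician who agrees. However, the permission itself covers pulmonary function and cardiopulmonary exercise tests without a visit limit, and Table 1 labels the visit 3 to 5 rides as CPET. It is an open permission, not a planned disclosure.
- **Guess rates.** Selection on a single-day threshold invites regression to the mean. Albuterol as needed continues throughout, and the overnight albuterol washout is stated only for visit 2, so rescue use could blur visit 3 to 5 values. The highest rates also need someone holding both visits' results.
- **Effect on AF.** PF and AF are measured against a same-day maximal-effort baseline. Encouragement that raises both efforts would partly cancel. Endurance time has no such same-day reference.
- **Other clues.** Inspiratory capacity is measured during the ride and immediately before the fatigue measurement, and endurance must be known to choose the visit 5 treatment. These are inherent in the design, and restricting spirometry does not remove them.

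**Conclusion.** The point holds as a missing safeguard. The plan states a blind to study end, but section 20 allows release of visit 3 to 5 results between crossover periods, and nothing keeps post-dose lung-function values from staff who encourage the efforts. How often treatment could be inferred is unknown. Under D of 6 to 20% and s of 5 to 15%, comparing visits 3 and 4 gives about 61% to over 99% correct. Comparing visit 3 with visit 2 gives 62 to 92% in the main cases worked, and 56% at the weakest corner. All of these rest on assumed inputs and an optimal guesser. Bias in AF is possible but not quantified. The documents do not support a conclusion that the blind is broken or that the AF result would be invalid. This is a cheap improvement.

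**What to change.** 1. **Section 20.** Add that no spirometry, lung-volume, inspiratory-capacity or endurance result from visits 3 to 5 is released to a patient until that patient has completed visit 5, except where needed for safety.
2. **Section 8 g, Visit schedule and Procedures.** Where the existing rota allows, have visit 3 to 5 spirometry and lung volumes run by a current team member who does not coach that visit's ride or isokinetic efforts. That person withholds the values until the patient's fatigue data are processed, again except for safety.

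**Cost.** Two protocol sentences and a rota. Section 7 already lists coordinators, post-doctoral scientists and a research associate. Sample size, visits and treatment do not change. Patients wait up to about 6 weeks for results (day 7 to day 49 in Table 1, 42 days), longer if a visit is repeated, and one team member is kept off coaching at each visit.

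**Limit.** Inspiratory capacity and endurance time stay visible to the exercise team, so the change lowers the risk of unblinding but does not remove it.

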- 8) Patients who have a limitation of exercise performance as a result of factors other than fatigue or exertional dyspnea, such as arthritis in the leg, angina pectoris or claudication or morbid obesity.
- 9) Patients with a constant power cycle ergometry endurance time less than 4 or greater than 10 minutes after work rate adjustment procedures (described below).
- 10) Patients who have taken an investigational drug within one month or six half-lives (whichever is greater) prior to screening visit (Visit 1).
- 11) Pregnant or nursing women.
- 12) Women of childbearing who have the potential not to be using a highly effective method of birth control. Female patients will be considered to be of childbearing potential unless surgically sterilized by hysterectomy or bilateral tubal ligation, or post-menopausal for at least two years.
- 13) Patients who are currently participating in another interventional study.
- 14) Patients who are unable to comply with pulmonary medication restrictions prior to randomization.

All subjects will be screened for eligibility during visits 1 and 2. Eligibility will be determined by medical history, physical examination, spirometry (visit 1) and exercise testing (visit 2). Women with the potential for pregnancy will be tested using a urine-based testing kit. Eligibility will be determined according to the study inclusion and exclusion criteria

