#### ***Visit schedule***

Written informed consent will be administered in the study center. Consenting subjects will discontinue long-acting bronchodilators for the entire duration of the study. All subjects will receive albuterol (either alone, or as a combination therapy; see below for details) to be taken as needed (prn) for the duration of the study. For those subjects prescribed long-acting antimuscarinic therapy at study entry, during the three washout periods of the protocol subject's therapy shall consist of combination albuterol and ipratropium (Combivent) prn. Patients taking a combination long-acting beta agonist and inhaled corticosteroid therapy (LABA+ICS) at study entry will be transitioned to ICS monotherapy for the duration of the study. The study drug (STIOLTO™ RESPIMAT® or placebo) will be administered daily during three 1-week periods during the protocol. Each time, the study drug will be taken for one week before testing is performed. The study timeline is shown in Figure 1. The study will require a total 5 visits by each patient for pulmonary function and exercise tests.

Visit 1: Baseline pulmonary function test. Visit 1 will occur after consent and will include full pulmonary function assessment including pre- and post-bronchodilator spirometry, resting ECG, and muscle NIRS test.

Visit 2: Baseline cardiopulmonary exercise tests. Visit 2 will include spirometry, an incremental exercise test, and a constant power exercise test on a cycle ergometer. This testing day will be preceded by a 14-day washout of all long acting bronchodilators, and an overnight washout of short-acting albuterol. COPD questionnaires will be completed.

PROTOCOL TITLE: A randomized, crossover, placebo controlled, double-blind phase IV trial of the effect of on STIOLTOTTM RESPIMAT® on central and peripheral components of fatigue during exercise in chronic obstructive pulmonary disease  
Revised: November 13, 2015

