### ***Medications***

***STIOLTOTTM RESPIMAT®***: Two actuations of STIOLTOTTM RESPIMAT®, taken once daily, provides 6.2 micrograms of tiotropium bromide monohydrate and 5.5 micrograms olodaterol hydrochloride, which is equivalent to 5.0 micrograms of tiotropium and 5.0 micrograms of olodaterol.

Tiotropium bromide is a non-chiral, long-acting, inhaled anticholinergic bronchodilator initially developed for the long-term, once-daily, maintenance treatment of bronchospasm and dyspnea associated with chronic obstructive pulmonary disease (COPD), including chronic bronchitis and emphysema. It has had FDA approval for use in COPD for over 10 years and is used in COPD more than any other bronchodilator medication.

Olodaterol hydrochloride is a long-acting beta2-adrenergic agonist bronchodilator indicated for the long-term, once-daily maintenance bronchodilator treatment of airflow obstruction in patients with chronic obstructive pulmonary disease (COPD), including chronic bronchitis and/or emphysema. It has had FDA approval for use in COPD for about 2 years.

PROTOCOL TITLE: A randomized, crossover, placebo controlled, double-blind phase IV trial of the effect of on STIOLTO™ RESPIMAT® on central and peripheral components of fatigue during exercise in chronic obstructive pulmonary disease  
Revised: November 13, 2015

The drug product, STIOLTO™ RESPIMAT® is composed of a sterile aqueous solution of tiotropium bromide and olodaterol hydrochloride filled into a 4.5 mL plastic container crimped into an aluminum cylinder (Stiolto™ cartridge) for use with the Stiolto™ Respimat® inhaler.

The drug package insert is attached to this application.

*Placebo Respimat®*: The placebo Respimat® inhaler will be prepared by the manufacturer and contains no active therapeutic agent.

*Albuterol*: Albuterol is an FDA approved medication for pulmonary function testing. It may be used in this study as a short-acting medication during washout periods. The drug package insert is attached to this application.

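### The overnight short-acting bronchodilator hold is written for visit 2 only; as-needed albuterol has no hold and no use record before the visit 3-5 tests that supply the primary comparison

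*Combined protocol and SAP*

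**What the plan says.** Section 8(g), Visit schedule, gives every patient albuterol "to be taken as needed (prn) for the duration of the study". For visit 2 it adds: "This testing day will be preceded by a 14-day washout of all long acting bronchodilators, and an overnight washout of short-acting albuterol". The description of the incremental exercise test in Procedures repeats that overnight hold, again for visit 2.

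For the randomized tests the same section says "Visits 3-5 will be preceded by a 14-day washout period and 7 days using once-daily" study treatment, and then "Subjects will take their daily dose of the study medication 90 minutes before undergoing spirometry and constant work rate testing". Nothing is said there about short-acting drug. The description of the constant work rate tests adds no hold either.

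Other relevant places:

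- Section 8(g), Medications, on albuterol: "It may be used in this study as a short-acting medication during washout periods". Section 9, on use of short-acting bronchodilators, likewise describes it as the replacement supplied for the 2-week washouts. Combivent is tied to the washouts in the Visit schedule, in Medications and in Section 9.
- Exclusion criterion 14: "Patients who are unable to comply with pulmonary medication restrictions prior to randomization". It does not reach the tests after randomization.
- Inclusion criterion 2: "At visit 1, patients will demonstrate appreciable reversibility, defined as a 12% increase in" FEV1 after albuterol.
- Table 1 has no row for rescue or concomitant medication. Medication history is collected at visit 1. Section 17 says supplementary drugs are supplied open-label as needed.
- The Analysis Plan has no rule for a test that followed recent albuterol.

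**The concern.** The trial contrasts bronchodilation with no bronchodilation, to see whether less dynamic hyperinflation goes with less AF. Albuterol shortly before a placebo test supplies some of that bronchodilation, and inclusion criterion 2 selects patients in whom it raises FEV1. Blinding and random order do not balance this, because as-needed use follows symptoms that arise after assignment.

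If patients reach for albuterol more often in placebo weeks, the placebo test lasts longer and shows less hyperinflation. The isotime point taken from it then falls later in the drug test. Both effects shrink the AF difference that carries the primary objective, and a null AF result could mean either no central effect or a placebo test partly treated.

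MF is exposed in another way. The Analysis Plan treats similar MF at drug isotime and placebo intolerance as agreement with the hypothesis. If a real MF difference exists, dilution pushes the result toward that predicted similarity.

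**Working it through.** **1. The text, side by side**

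| Item | Visit 2 | Visits 3-5 |
|---|---|---|
| Long-acting washout | 14 days | 14 days, then 7 days of study drug |
| Short-acting hold | Overnight, stated twice | None stated |
| Test-day dosing rule | Not applicable | Study drug 90 minutes before testing |
| Albuterol as needed | Yes, whole study | Yes in Visit schedule; Medications and Section 9 suggest washouts only |
| Planned record of rescue use | None | None |

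The Medications sentence is permissive and conflicts with the Visit schedule. Even on its narrower reading there is no pre-test hold and no instruction for a patient who needs rescue that morning.

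**2. The plan's own power figure**

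Inputs from Section 8(i), Power calculation: f = 0.23, r = 0.80, n = 21, alpha = 0.05, stated power 0.95. The number of repeated measurements m is not stated, nor is the sidedness of alpha.

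- Within-subject ANOVA: lambda = n × m × f² / (1 − r). With m = 3, lambda = 21 × 3 × 0.0529 / 0.20 = 16.66 on 2 and 40 degrees of freedom, giving power 0.950. This matches.
- Planned paired t-test, taken as two-sided: dz = 2f / √(2(1 − r)) = 0.46 / √0.40 = 0.727. Noncentrality = 0.727 × √21 = 3.333 on 20 degrees of freedom, giving power 0.887.

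**3. Illustrative dilution**

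Assumptions, none of them in the documents: a share q of placebo tests follows albuterol, those tests lose a share s of the drug-placebo difference, no drug test is affected, and the SD of the differences is unchanged. The effect is then multiplied by (1 − q × s).

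| q | s | q × s | dz | Power, paired t | Power, ANOVA m = 3 |
|---|---|---|---|---|---|
| 0 | – | 0 | 0.727 | 0.887 | 0.950 |
| 10% | 50% | 0.05 | 0.691 | 0.853 | 0.927 |
| 10% | 100% | 0.10 | 0.655 | 0.814 | 0.896 |
| 25% | 50% | 0.125 | 0.636 | 0.792 | 0.878 |
| 25% | 100% | 0.25 | 0.545 | 0.662 | 0.755 |
| 50% | 100% | 0.50 | 0.364 | 0.355 | 0.403 |

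Power reaches 0.80 at q × s of about 0.116 for the paired t-test and about 0.21 for the three-measurement ANOVA. The last row is an outer bound: half of placebo tests would follow a rescue dose that reproduces the whole effect of a week of dual long-acting treatment. Nothing in the documents supports that. With no pre-test use, nothing changes.

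**The case against.** **The plan may already confine albuterol to the washouts.** Medications and Section 9 point that way, and the conflict with the Visit schedule may be a drafting slip rather than a decision to permit albuterol before tests. This stands in part. For Combivent the washout restriction is consistent, so the live gap is albuterol. For albuterol the reader still meets two instructions and no hold under either.

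**Affected tests would not be wholly invisible.** Spirometry precedes each exercise test and resting inspiratory capacity is measured, so after unblinding placebo-day values can be compared with visit 2, where albuterol was held. This stands: a reader might infer that affected tests could never be recognised, and that goes too far. It is a partial check that does not replace a recorded dose and time.

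**The size is assumed.** This stands. FEV1 reversibility does not establish an effect of albuterol on hyperinflation, endurance or AF, and no rescue rate is given.

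**A reader might infer that the error can only be conservative.** The documents do not support that. Albuterol before a drug test would push the other way, and dilution of MF moves toward the predicted result.

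**A reader might also blame albuterol if placebo turns out to be the longer test and is repeated at visit 5.** Ordinary test-to-test variation can produce that under the plan's rule without any albuterol, so it is not counted here. Nor does the visit 2 hold by itself bias visit 3 against visit 4: visit 2 sets the work rate and familiarises the patient.

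**Conclusion.** The omission is real. The hold exists for the visit that sets the work rate and is absent for the visits that supply the primary comparison, while albuterol remains available as needed under the Visit schedule.

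The consequence is conditional. Dilution of the contrast in hyperinflation, endurance and AF requires albuterol use before tests that is heavier on placebo than on drug. Under the same condition, the similar-MF prediction could be falsely supported. Neither the frequency of use nor its effect can be derived from the documents, so the power figures show sensitivity and are not an estimate of harm. The correction should be made because it is cheap before enrolment, and a missed record of use cannot be reliably rebuilt afterwards.

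**What to change.** - In the visits 3-5 paragraph of the Visit schedule, apply the same overnight short-acting hold as at visit 2.
- Reconcile the Visit schedule with Medications and Section 9 on whether albuterol is available during the dosing weeks.
- Add a Table 1 row for the time and number of puffs of the last rescue dose at each test visit, and report it by condition.
- State that a patient who needs rescue takes it and that, where feasible, the test is rescheduled once under the existing repeat-visit rule, on the same condition. The limit of one matters: repeats driven by symptoms would probably fall more on placebo and lengthen exposure unequally.
- Keep all tests in the primary analysis. Excluding rescue-affected tests conditions on a post-randomization event and discards pairs from 21 patients, so such an analysis is supportive only.

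Cost: an overnight hold before three more visits in patients with FEV1 below 50% of predicted, and some repeat visits. If 10% to 25% of the 21 × 3 = 63 test visits were repeated (assumption), that is 6.3 to 15.75 repeats, or about $630 to $1,575 in participant payments at the $100 per visit in Section 13. These come on top of the roughly 15% technical repeats seen in the previous study. Staff time and extra study drug are additional. A repeat in a placebo phase adds up to about a week off long-acting therapy.
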